### 8.3 Reporting of Adverse Events

In the event of an SAE, SADE, USADE or device deficiency that could have led to an SAE, the Investigator must report the event using the appropriate form to the Sponsor Adverse Event Management Team (AEMT) by email: [REDACTED] including in the email vendor and Sponsor Study Managers within 24 hours of knowledge of the event.

The out of hours emergency phone number is [REDACTED] if consultation is required by the Investigator.

This emergency phone number will be confirmed to the Investigator at the Investigation Initiation Visit.

All forms of SAE / SADE / USADE and Device Deficiency that could have led to a SAE/ SADE/ USADE must be provided via email. Any inconsistencies in the information received from the Investigator will be clarified on an updated SAE / SADE form. The Investigator must retain a copy of all the forms in the Investigator Site File.

The Investigator, if required by regulations, must inform their local Independent Ethics Committee (IEC) / Research Ethics Committee (REC) / Institutional Review Board (IRB) of all SAE / SADE / USADEs and reportable Device Deficiencies occurring in the investigation as per Sponsor instructions as described in the Safety Management Plan.

SAE / SADE / USADEs, Device Deficiencies and non-serious AE / ADEs will be reported to the appropriate regulatory authorities by the Sponsor in accordance with the authorities' requirements. The Sponsor is responsible for expedited reporting of all SAE / SADE / USADEs and reportable Device Deficiencies to relevant authorities and IECs / IRBs as required by regulations. If the event requires expedited reporting, AEMT will take actions as per the investigation specific Safety Management Plan.

Reporting timelines for reporting USADEs / SAE / SADE / Device Deficiencies that could have led to a SAE/ SADE/ USADE to the Competent Authority (CA) is:

- immediately or within 2 calendar days from initial receipt for reportable events or of new information in relation with an already reported event which indicate imminent risk of death, serious injury, or serious illness and that requires prompt remedial action for other patients/subjects, users or other persons or a new finding to it.
- Any other reportable events, reporting timeline is immediately, but not later than 7 calendar days following the date of awareness by the sponsor of the new reportable event or of new information in relation with an already reported event.

If a reportable USADE / SAE / SADE / Device Deficiency occurs, AEMT will use the USADE Reporting Contact List for details of who and where to send details to the country where this is the case is Germany. The AEMT will provide the completed Manufacturer Incident Report (MIR) form to the Drug Safety Officer (DSO) who will complete the German SAE Report form in English, based on the information provided in the MIR, and send to the Competent Authority via email.

Reporting timelines for reporting SADE / Device Deficiencies that could have led to a SAE/ SADE/ USADE to the Notified Body is immediately but no later than 1 working day of reporting to the

	Clinical Investigation Plan		
	Investigation No: 5078401	Protocol Version: V2.0 08-Jun-2023	Page 50 of 62

Competent Authority. (This is only required for CE marked products: Test Condom A and Control NRL Condom).

The CA expects a quarterly summary on all reportable SAE/SADE/Device Deficiencies and in addition SAE/SADE/Device Deficiencies that are included in the endpoints according to the CIP.

The Investigator must report all reportable events to the sponsor immediately but not later than 24 hours after investigational site investigation personnel's awareness of the event.

The Investigator should not break the randomisation code except when it is necessary to do so in order to ensure the subject receives appropriate medical care.

#### **8.4 Follow-up of Adverse Events**

All SAE / SADE / USADEs and all AE / ADEs that have not resolved by the end of the investigation will be followed up by the Investigator until resolution or until the Investigator believes there will be no further change, whichever is the earlier. This may involve the subject or the female partner making additional visits to the site.

In the case of loss to follow-up, at least two documented attempts to contact the subject must be made by the Investigator or designee before this is defined.

The end of the investigation is defined as the last visit of the last subject in the investigation.

All SAE/ SADE/ USADEs and all AE/ ADE that cause premature withdrawal of the subject and the female partner from the investigation and have not resolved by the end of the investigation will be followed up by the Investigator until resolution or until the Investigator believes there will be no further change.

This may involve the subject or the female partner making additional visits to the site. The minimum data required are the subject number, suspected investigational product, final outcome and date, which may be obtained by the Investigator in a documented telephone conversation with the subject/female partner or subject's/female partner's general practitioner (GP)/ Primary Care Physician (PCP).

Subjects/Female partners who experience the onset of an (S)AE after the last visit (end of the investigation) will not need to be recorded.

#### **8.5 Misuse and Medical Device administration Errors**

The Sponsor defines "misuse" as situations where the medical device is intentionally and inappropriately used not in accordance with the authorised product information.

All incidences of misuse are reportable to the Sponsor irrespective of the presence of an associated AE. The misuse and any associated untoward event will be captured on an AE / ADE CRF page or on a SAE / SADE / USADE form.

Medical device administration errors are any unintentional errors in administration which relates to:

- Using / being administered an incorrect medical device
- Using / being administered the medical device by the wrong route of administration / application

	Clinical Investigation Plan		
	Investigation No: 5078401	Protocol Version: V2.0 08-Jun-2023	Page 51 of 62

- The accidental administration of the medical device to a person who is not a subject within the investigation

Medical device administration errors are reportable to the Sponsor irrespective of the presence of an associated AE. Medical device administration errors with or without an associated untoward event will be captured on an AE / ADE eCRF page or on a SAE / SADE / USADE form.

In all cases of misuses and administration errors, in the judgement of the Investigator, the Investigator can withdraw the subject if the event effects the subject's/female partner's safety. Follow-up assessments should be conducted as described for the follow-up visit ([Section 7.5](#)).

## 8.6 Pregnancy

Pregnancy in the female partner of a male subject is considered a collectable event and will be recorded as an AE in all cases. It will be qualified as an SAE only if it fulfils SAE criteria.

The subject, whose female partner is pregnant, must immediately be withdrawn from the clinical investigation and the Sponsor must be promptly notified of the event. Any pregnancy during the investigation will be reported to the Sponsor within 24 hours of becoming aware of the pregnancy. The course and outcome of the pregnancy should be followed up carefully by the Sponsor Pharmacovigilance personnel, DSO, as part of their safety monitoring responsibilities and will not form part of the investigation dataset. The Sponsor Pharmacovigilance will liaise with the Investigator via the Sponsor's clinical study manager for follow up with the subject. Three documented follow up attempts should be made.

Any abnormal outcome regarding the mother or the child should be documented and reported.

## 9 STATISTICAL CONSIDERATIONS

This section presents a summary of the planned statistical analyses. A statistical analysis plan (SAP) that describes the details of the analyses to be conducted will be written prior to database lock.

Summary statistics for continuous variables will typically include the number of subjects (n), mean, standard deviation (SD), median, minimum and maximum. For categorical variables, summary statistics will typically include the number and percentage of patients in each category. All data will be presented in listings.

Baseline values are defined as the last measurements taken before administration of the randomised product.

### 9.1 Statistical Analysis Plan

Details of statistical methods and analysis will be documented in the SAP.

If there are any deviations to the proposed statistical analysis as described in this protocol these will either be documented in a protocol amendment and / or the final SAP prior to database lock with the rationale and impact of the changes addressed.

	Clinical Investigation Plan		
	Investigation No: 5078401	Protocol Version: V2.0 08-Jun-2023	Page 52 of 62

## 9.2 Interim Analysis

No interim analysis is planned.

## 9.3 Analysis Datasets

The analysis populations will be as follows:

- The safety population will include all randomised subjects who use at least one of the study condoms. The safety population will be used for all baseline summaries and summary of safety data. For the safety population, subjects will be analysed according to treatment received. The Full Analysis Set (FAS) will include all randomised subjects who use at least one of the study condoms and who have IELT recorded in at least one of the post-baseline study periods. The FAS will be used for the analysis of all efficacy endpoints. For the FAS, subjects will be analysed according to their randomised treatment.
- The Per Protocol (PP) population will consist of all patients in the FAS who do not deviate from the protocol in such a way as to impact the evaluation of the primary endpoint. Subjects who do not have an IELT recorded for at least 4 condom uses within a treatment period will be excluded from the PP population for that period. All decisions on exclusions from the PP population will be made prior to database lock. For the PP population, subjects will be analysed according to treatment received.

## 9.4 Subject Disposition and Characteristics

The number of subjects screened, randomised, completing, and withdrawing, along with reasons for withdrawal, will be tabulated. The number of subjects in each analysis population will be reported. Demographic and baseline characteristics (including age, gender, ethnicity, weight, height and BMI) will be summarised using descriptive statistics. No formal statistical analysis will be performed.

## 9.5 Statistical Analyses

All statistical analysis will be performed using SAS® version 9.4 or higher. For all endpoints, in the event that the assumptions underlying the parametric approach are violated, alternative non-parametric methods will be used.

### 9.5.1 Primary Endpoint(s)

#### 9.5.1.1 Primary Analysis

The primary endpoint of the investigation is the change from baseline in IELT with the 5% Benzocaine condom versus the standard NRL condom, over a 4-week assessment period. For each subject, a mean IELT will be calculated across all intercourse episodes within a study period (baseline, assessment period 1, assessment period 2 and assessment period 3) and used for analysis. The change from baseline in IELT will be analysed using a linear mixed model using data from all three condom groups, with the primary comparison between the 5% benzocaine condom

	Clinical Investigation Plan		
	Investigation No: 5078401	Protocol Version: V2.0 08-Jun-2023	Page 53 of 62

with the standard NRL condom. The model will include fixed effects for treatment and period, a covariate for baseline IELT, and subject as a random effect. The differences between the 5% benzocaine condom with the standard NRL condom will be presented with a 95% CI and an associated p-value. Statistical significance will be assessed at the two-sided 5% level. No adjustment for multiplicity will be made since there is a single primary comparison (5% benzocaine condom versus standard NRL condom). No assumptions of normality will be checked based upon the utilization of the Generalized Linear Mixed Model (GLMM) to analyse the primary endpoint. If the model can't handle the violation, then worst case scenario a non-parametric model will be used, such as Wilcoxon signed ranks test with Hodges Lehmann estimator for treatment differences.

### 9.5.1.2 Secondary Analysis

In the event of any protocol deviations that warrant exclusion from the FAS, an analysis of the primary endpoint based on the PP population will be performed.

## 9.5.2 Secondary Endpoint(s)

All secondary endpoints will be evaluated based on comparing the 5% and 3% benzocaine condoms with the standard NRL condom. No adjustment for multiplicity is planned for the secondary endpoints, and so p-values will be interpreted with appropriate consideration of Type I error.

### 9.5.2.1 Secondary Endpoint Analyses

The secondary endpoints of the investigation are:

- Change from baseline in IELT with the 3% Benzocaine condom compared to the standard NRL Condom, over a 4-week assessment period.
- Proportion of subjects who achieve an increase of 2 mins from baseline in IELT in the 5% and 3% benzocaine condoms compared to the standard NRL Condom.
- Proportion of subjects who achieve an increase of 3 mins from baseline in IELT in the 5% and 3% benzocaine condoms compared to the standard NRL Condom.
- Proportion of subjects who achieve an increase of 4 mins from baseline in IELT in the 5% and 3% benzocaine condoms compared to the standard NRL Condom.
- A measure of Patient Global Impression of Change (PGIC) at the end of each 4-week assessment period, in subjects using the 5% and 3% benzocaine condoms compared to the standard NRL Condom.
- A measure of EMSEX pleasure scale at the end of each 4-week assessment period, in subjects using the 5% and 3% benzocaine condoms compared to the standard NRL Condom.
- User acceptability, experience and preference of each condom type will be evaluated through subject perceived questions, asked at the end of each 4-week assessment period.

	Clinical Investigation Plan		
	Investigation No: 5078401	Protocol Version: V2.0 08-Jun-2023	Page 54 of 62

- The in-use tolerability of each condom type will be evaluated through subject perceived questions, asked at the end of each 4-week assessment period.
- A measure of the total clinical failure rate of Test Condom A, Test Condom B and Control NRL condom.
- Overall proportion of subjects with Adverse Events/ Adverse Device Effects (AEs/ ADEs), i.e. the occurrence of one or more AEs/ ADEs per subject.

The change from baseline IELT with the 3% benzocaine condom compared to the standard NRL condom will be evaluated using the same linear mixed model as for the primary endpoint. The difference in least square means and associated 95% CI will be calculated, with a p-value to assess statistical significance.

The proportion of subjects who achieve an increase of 2, 3 or 4 mins from baseline in IELT (calculated from the mean across all intercourse episodes within a period) will be calculated for each condom type. The proportion achieving an increase of 2, 3 or 4 mins will be compared for the 5% and 3% benzocaine condoms versus the standard NRL condom using a GLMM with marginal means under the assumption that the mean of the outcome variable (1=success or 0=failure) follows a binomial distribution. Factors in the model will include fixed effects for treatment and period, and baseline IELT as a covariate. Subject will be included as a random effect. Comparison between the 5% and 3% Benzocaine condoms with the standard NRL condom will be expressed as an odds ratio, with an associated 95% CI and p-value.

The PGIC recorded at the end of each condom assessment period will be summarised by condom type, as the number and percentage in each category of the PGIC (Very much better, Better, Little better, No change, Little worse, Worse, Very much worse). A comparison of the PGIC in each of the 5% and 3% Benzocaine condoms versus the standard NRL condom will be performed using a GLMM, assuming a multinomial distribution for the response variable. Factors in the model will include fixed effects for treatment and period. Subject will be included as a random effect. Comparison between the 5% and 3% Benzocaine condoms with the standard NRL condom will be expressed as an odds ratio, with an associated 95% CI and p-value. In the event that some categories of the PGIC have too few subjects for the model to fit, the number of categories in the PGIC responses may be reduced (e.g. better, no change, worse) for purposes of analysis.

After each coital act, the mean of the responses on the EMSEX pleasure scale (0 to 100) will be calculated as the sum of responses divided by number of questions answered. For each condom assessment period, a subject-level mean EMSEX pleasure scale will then be derived using data from all coital acts. The EMSEX pleasure scale score will be analysed using a linear mixed model using data from all three condom groups, with comparisons between the 5% and 3% Benzocaine condoms with the standard NRL condom. The model will include fixed effects for treatment and period, and subject as a random effect. The between group differences will be presented with a 95% CI and an associated p-value.

Responses to SPQs will be summarised for each condom type using descriptive statistics.

	Clinical Investigation Plan		
	Investigation No: 5078401	Protocol Version: V2.0 08-Jun-2023	Page 55 of 62

### 9.5.3 Descriptive Statistics and Listings

All data (including vital signs, physical exam, number of intercourse episodes for each condom type and IELT) will be summarised using descriptive statistics where appropriate, and subject-level data will be provided in data listings.

### 9.6 Adverse Events

Safety endpoints will include incidence of treatment-emergent AEs (TE AEs), ADEs (TE ADEs) and concomitant medications. An AE will be considered treatment emergent if it started after the first condom used. Data listings will be provided for CIP-specified safety data. MedDRA (Version 26.0 or the most recent version if this has changed during the course of the clinical investigation) will be used to code all AEs with respect to system organ class and preferred term. AE summaries will include only TE AEs and TE ADEs, which will be summarised (incidence and frequency) separately for males and females, by treatment group. Treatment-emergent AEs and ADEs will also be summarised by severity and relationship to randomised treatment (condom type) and by relationship to the investigational procedure.

Concomitant medication usage will be listed and summarised by coded term separately for males and females, by treatment group.

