## 6.11 Adverse Events

During visits to the clinical site non-leading questions will be used to collect any AEs/ ADEs. In addition, spontaneously reported AEs/ ADEs will be collected.

The observation period for an individual subject and his female partner will start after giving informed consent and will finish at the last visit (follow-up visit). All AEs/ ADEs that arise during the observation period will be recorded and an assessment of the AEs/ ADEs will be performed as per [Section 8.2](#) by a medically qualified Investigator. If a subject or his female partner has an AE/ ADE that is still ongoing at the last visit, an attempt will be made by the Investigator to follow this up as per [Section 8.4](#).

If an untoward medical occurrence happens after the subject has signed the consent form but before administration of the device, it should be reported as an AE, including those associated with investigation procedures.

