## **9.2 Variables evaluated for safety analysis**

### **(Serious) Adverse Events / Adverse Device Effects**

(Serious) Adverse events (S)AEs or Adverse Device Effects (S)ADEs, as reported spontaneously by the subject or observed by the Investigator, recorded in the course of the clinical investigation will be described individually. The following data will be compiled in the (e)CRF:

- Screening number
- AE/ADE number
- Did the subject/partner experience any AEs/ADEs? [yes/no]
- Type of Event [AE/ADE]
- Is this a device deficiency (DD)? [yes/no]
- AE/ADE description [free text]
- Date and time AE/ADE started [dd.mm.yyyy – hh:mm]
- Severity [Mild/Moderate/Severe]

- Any changes in AE/ADE severity? [yes/no]
- Comment the changes if “yes”
- Date of change in severity [dd.mm.yyyy]
- Time of change in severity [hh:mm]
- New severity [mild/moderate/severe]
- Frequency [single episode/intermittant/continuous]
- Action taken (device) [no change/use increased/use reduced/device withdrawn or use stopped/not applicable.
- Action taken (subject) [symptomatic therapy or treatment/subject hospitalised or hospitalisation prolonged/none/other action]
- Specification if “other” was chosen [free text]
- Has the subject been withdrawn from the study due to this AE/ADE? [yes/no]
- Were any concomitant medications taken in association with this AE/ADE? [yes/no]
- Relationship to device (investigator)[causal relationship/probable/possible/not related]
- Is the adverse event/ adverse device effect serious? [yes/no]
- Reasons for being serious [Selection if suitable]
  - Led to death
  - Led to serious deterioration of health that either
    - resulted in a life-threatening illness or injury
    - resulted in a permanent impairment of a body structure or a body function
    - required in-patient hospitalisation or prolongation of existing hospitalization
    - resulted in medical or surgical intervention to prevent life threatening illness or injury or permanent impairment to a body structure or function
  - Led to foetal distress, foetal death or a congenital abnormality or birth defect
  - Device deficiency that may have led to a serious adverse event if
    - Suitable action had not been taken
    - Intervention had not been made
    - If circumstances had been less fortunate
- Is the AE/ ADE ongoing? [yes/no]
- If no, date and time resolved [dd.mm.yyyy – hh:mm]

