## 11 Statistical methods

### 11.1 Dichotomous and categorical variables

For all dichotomous and categorical variables, absolute and relative frequencies will be calculated if not stated otherwise.

For safety variables – separated by subject and partner:

Two separate counting rules apply for AEs:

- Total number of AEs (possibly counting subjects with several AEs more than once)
- Total and relative number of subjects suffering from at least one AE
- The overall proportion of AE subjects with last safety objective

Frequencies of AEs will be summarized in tables overall, by system organ class (SOC) and preferred term (PT) based on MedDRA Coding (Version 26.1 or higher) including only TE AEs and TE ADEs, which will be summarized (incidence and frequency) separately for males and females, by treatment group.

Two separate counting rules apply for changes in prior and concomitant therapies:

- Total number of changes in concomitant therapies (possibly counting subjects more than once)
- Total and relative number of subjects receiving at least one change in concomitant therapies.

Two separate counting rules apply for concomitant diagnoses:

- Total number of diagnoses/therapies (possibly counting subjects more than once)
- Total and relative number of subjects having at least one diagnosis/therapies. ,

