### 14.3. Safety Data (SP)

#### 14.3.1. *Display of adverse events of subject and partner*

*Table 14.3.1.1* Counts and percentages of TE-AEs/ADEs and subjects with TE-AEs/ADEs

*Table 14.3.1.2* Counts and percentages of AEs/ADEs and subjects with TE-AEs/ADEs by SOC and PT

*Table 14.3.1.3* Counts and percentages of TE-AEs/ADEs: relationship to IP

*Table 14.3.1.4* Counts and percentages of TE-AEs/ADEs: severity

*Table 14.3.1.5* Counts and percentages of TE- AEs/ADEs: action taken ( subject)

*Table 14.3.1.6* Counts and percentages of TE-AEs/ADEs: outcome

*Table 14.3.1.7* Counts and percentages of subject withdrawn due to TE-AE/ADE

*Table 14.3.1.8* Counts and percentages of TE-AEs/ADEs: serious adverse event

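### Treatment-emergence has no worsening clause, and no rule says which condom takes an adverse event that spans crossover periods

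*Protocol*

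**What the plan says.** Protocol 9.6 holds the only definition: "An AE will be considered treatment emergent if it started after the first condom used". It then restricts the output: "AE summaries will include only TE AEs and TE ADEs", split by treatment group. SAP 11.1 carries the restriction over, with tables "including only TE AEs and TE ADEs, which will be summarized (incidence and frequency) separately for males and females, by treatment group". It does not define the term, and SAP 15 declares no departure from the protocol.

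Collection begins much earlier than the cut-off. Under Protocol 6.11, "The observation period for an individual subject and his female partner will start after giving informed consent", so it covers the 4-week baseline period before any study condom is issued.

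On treatment assignment, Protocol 9.3 says "For the safety population, subjects will be analysed according to treatment received", and SAP 8 says the same. SAP 9.2 lists the AE form: onset date and time, severity, whether severity changed, the date ("Date of change in severity [dd.mm.yyyy") and time of the change, and the new severity. Among the planned safety tables is "Counts and percentages of TE-AEs/ADEs: severity" (SAP 19.4, Table 14.3.1.4).

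**The concern.** A rule based on onset alone cannot see aggravation. In a three-period crossover with AE tables by condom, two questions need an answer: does the event count, and under which condom? The protocol answers the first by onset against a single cut-off. Neither document answers the second for an event that continues into a later period.

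Protocol 1.7 names local irritation as a known reaction to both latex condoms and benzocaine. A pre-existing irritation made worse by a medicated condom is therefore an event the safety comparison ought to show. The proportion of subjects with AEs or ADEs is a secondary endpoint and is to be tabulated for each condom (SAP Table 14.2.2.26). If aggravated reactions are left out, or placed by an unwritten convention chosen after the randomisation list is merged (SAP 10.2), that comparison is less reliable than it looks.

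**Working it through.** The plan states no figure that depends on this definition, so there is none to reproduce. The check applies the written rule to three illustrative histories and then counts the sequences.

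**Applying the rule**

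1. *Mild irritation starts in baseline and becomes moderate during the Test Condom A period.* Onset is before the first study condom, so the event is not treatment-emergent. Protocol 9.6 and SAP 11.1 then keep it out of the summaries. It stays in the listings, because all data are listed (Protocol 9, SAP 19.5). The dated severity change is on the form, but no rule uses it.
2. *Mild irritation starts on the control condom in period 1 and becomes severe on Test Condom A in period 2.* Onset is after the first study condom, so the event is treatment-emergent and is not dropped. The column it goes in is not stated. Nor is it stated whether the severity table takes the initial or the new severity. If assignment were by onset with the worst severity, control would show one severe event and A none. If assignment were by dated change, control would show a mild event and A a severe one.
3. *An event starts during the 3-day washout.* It is treatment-emergent, and again its column is not stated.

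The AE fields in SAP 9.2 include no condom, kit or period, whereas the device-deficiency fields do ask for the kit. The condom must therefore be derived from dates, and no derivation is given. Analysis by treatment received does not supply one, because in a crossover each completing subject receives all three condoms.

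**Counting the sequences**

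Inputs: six sequences (Protocol 6.2, SAP 12.8) and 150 randomised (Protocol 4.5). Assumption: equal allocation, 150/6 = 25 per sequence. With C for control, the sequences are ABC, ACB, BAC, BCA, CAB and CBA.

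- A in period 2 or 3: 4 of 6, so 4 × 25 = 100 subjects.
- Control before A: BCA, CAB, CBA, so 3 × 25 = 75 subjects.
- A before control: ABC, ACB, BAC, so 3 × 25 = 75 subjects.
- Some study condom before a later benzocaine condom: 6 of 6, so 150 subjects.

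These are subjects in whom an event could carry over from one condom to another. No rate of onset or worsening is given, so the number of events affected cannot be computed.

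**The case against.** The strongest reply is that the cut-off decides only whether an event is treatment-emergent; it assigns nothing to a condom. A reader might infer that a reaction worsening on a later benzocaine condom is dropped, or charged to the control. The documents do not support either reading. Such an event is already treatment-emergent, and no section assigns it to the earlier condom. Even under assignment by onset the error would run both ways: in the 75 subjects with A before control, worsening on control would be credited to A. This part of the reply stands. The defect is an undefined attribution, not a demonstrated bias towards one condom.

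It can also be said that the baseline case is narrow. The event must persist and then worsen, eligibility is reconfirmed at Visits 2 to 4, the listings keep every event, and serious events are to have narratives. That limits the frequency and means the data are not lost, but the summaries still omit the event. Some SAP items lack the treatment-emergent qualifier: the proportion formula in 10.5, the topline list in 17, and part of the title of Table 14.3.1.2. The governing text in Protocol 9.6 and SAP 11.1 has it, as does Table 14.2.2.26, which reports the proportion.

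A site might open a new record for an aggravated reaction, which would give it its own onset. The severity-change fields suggest a single record, but neither document requires one.

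Finally, the cut-off does not say *study* condom, and commercial condoms may be used in baseline. This is minor. Protocol 9.3 and SAP 8 refer to study condoms, and the literal reading would make more events treatment-emergent, not fewer.

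**Conclusion.** The point holds in two parts. First, the stated rule leaves out of every AE summary an event that starts between consent and first study-condom use and then worsens on a study condom. This rests on the worsening being kept in the original AE record, as the form's fields suggest, and on SAP 11.1 governing the tables. Second, attribution of events that span or worsen across periods is undefined in both documents.

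The size is unknown. The counts of 100, 75 and 150 show where the situation is possible and should not be read as affected subjects or as a bias estimate. The primary IELT analysis and the success criterion are untouched. The change is still worth making: the written rule can under-report aggravated local reactions, and the information to avoid this is already being collected.

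**What to change.** Amend SAP 11.1 before database lock, for male subjects and female partners alike:

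- Define a treatment-emergent AE or ADE as one that starts, or increases in severity, after first use of a study condom.
- Assign each onset or worsening to the condom type most recently used at that time, including during washout.
- In the severity table, count the severity reached under that condom.
- Derive all of this from the onset and severity-change dates and times in the eCRF and the times of use in the IELT diary.

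Protocol 9.1 allows such a departure to be documented in the final SAP before lock, with rationale and impact. SAP 15, which now reports no changes, would need a matching entry. The cost is SAP wording and one derivation, with no new data, visits or subjects. The small downside is that one AE record can count under two condoms if it worsens, so table footnotes should say so.
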